5.4 Administration and Accountability

The survey questionnaires will be administered by trained staff that will be blinded to group assignment. Responses will be inputted by a study coordinator into a secure electronic database. All data will be monitored periodically to assure accuracy.

Patients will be assigned case numbers at the time of enrollment. The key explaining the linkage between patients' PHI and case number will be kept in another password protected computer so that each patients' PHI is well protected. Surveys responders will be identified via a case assignment number. Subject responses will be recorded on a standard form that will be kept on a password protected computer during the study period. Any clinical data that is abstract from the electronic medical record for each patient will also be recorded in a standard form which identifies patients only by their case numbers.

5.5 Subject Compliance Monitoring

Patients will be called at 7, 30, and 90 days following discharge to evaluate their response to the questionnaires. Incomplete response at 7 days will not preclude a phone call directed to patients at 30 and 90 days. Patients who are not reachable via phone interview will not undergo an analysis of their clinical data due to lack of consent.

5.5.1 Return or Destruction of Investigational Product

Completion of data collection will occur when all patients enrolled in the study have completed the study and are greater than 90 days from discharge. All response data as well as clinical data will be destroyed after data analysis. Study completion will be defined as completion of the analysis.

6 Study Procedures

At follow up phone calls, interviews will be conducted with results of questionnaires recorded after consent is obtained. Consent for abstraction of clinical data collected during routine care from the electronic medical record will also be obtained.

TABLE 1: SCHEDULE OF STUDY PROCEDURES

Study Phase	Screening	Intervention	Follow-up
--------------------	------------------	---------------------	------------------

Visit Number		1			
Study Days	0	Variable (depends on patient length of stay)	7 from discharge (+/- 3 days)	30 from discharge (+/- 7 days)	90 from discharge (+/- 14 days)
Informed Consent/Assent			X		
Review Inclusion/Exclusion Criteria	X				
Demographics/Medical History		X			
Physical Examination		X			
Pregnancy Test	X				
Prior/Concomitant Medications		X			
Treatment allocation		X			
Health Literacy Screen		X	X		
Morisky medication adherence			X	X	X
Stroke Patient Education Retention (SPER)			X		X
13 Likert style questionnaire			X		X
2 Modified Euroqol global quality of health questions			X		X
Stroke Impact Scale				X	
Readmission question			X	X	X
Unanticipated Problems Assessment			X	X	X
Nurse attending document		X			

6.1 Screening

Patients will be screened for trial enrollment upon arrival to the floor. All of the below are obtained at admission for all patients as part of standard of care procedures.

- Physical Exam including mental status evaluation (standard of care)
- Diagnosis (standard of care)
- Baseline functional status (standard of care)

6.2 Study Intervention Phase

If patients satisfy inclusion criteria and lack exclusion criteria they will be assigned to the intervention arm or the control arm depending on their admission date. The intervention phase will be the duration of the patient's hospital stay.

No research related procedures that differ from standard of care will be conducted as this is a comparative effectiveness trial.

6.3 Follow Up Phase of the Study

Follow-up visits will be conducted by telephone only. Informed consent for phone interviews will be obtained prior to the interview. Consent will also be obtained for data collection from the patients Hospital of the University of Pennsylvania electronic medical record. Whether the patient, a family member, or other person is answering the pertinent survey questions will be recorded. Patients may become fatigued when answering the survey questions in which case they can simply ask to stop and the phone conversation will end.

6.3.1 7 days following discharge

At 7 days after hospital discharge, the MMAS-4, SPER, the exploratory 13 Likert-style questions and two modified overall health questions will be administered. There are no well validated surveys regarding the inpatient experience that are patient centered and stroke specific so we designed 13 questions which focus on subject's perception of their inpatient stay as well questions designed to assess quality of life following stroke. The newly devised Likert-style questions as well as the 2 modified overall quality of health questions have been reviewed by a stroke-survivor in her role as patient advocate who was cared for at our institution. The single health literacy question will also be repeated at the 7 day follow up visit and interviewees will be asked about readmission. Though ideally patients will answer all survey questions themselves, responses to survey questions will be accepted from a legal representative provided they can answer accurately. Each interviewee will be identified based on their relationship to the patient on survey collection forms.

6.3.2 30 days following discharge

At 30 days following hospital discharge, the SIS and the MMAS-4 will be administered. Inquiry as to whether or not the patient has been readmitted will occur.

6.3.3 90 days following discharge

At 90 days following hospital discharge, the MMAS-4, SPER, the exploratory 13 Likert-style questions and the 2 modified global quality of health questions will be administered again. Patients will also be asked about any readmissions.

6.4 *Unscheduled Visits*

Clinic visits and other unscheduled visits will not replace phone interviews and will be entirely separate from this study.

6.5 *Subject Withdrawal*

Patients may withdraw from the study at any time without impact to their care. Patients may also be discontinued from the study at the discretion of the PIs for lack of adherence to intervention or study procedures or difficulty obtaining follow up or unexpected events. The PI may also withdraw patients who violate the study plan, or to protect the subject for reasons of safety or for administrative reasons. It will be documented whether or not each subject completes the study.

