3.1.2 Study Intervention Phase

All of the standard medical care will be identical in both arms of the study. Health literacy will be assessed in all patients upon admission to assure educational interventions are directed accordingly. Patients who

are assigned to standard nursing care will receive standard care which includes educational interventions from staff nurses in keeping with current Joint commission and AHA/ASA guidelines. Patients assigned to routine care will not interact with the attending nurse. Patients who are assigned to the intervention will receive additional patient-centered supplementary care and education from the attending nurse.

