5.3 Blinding

The 7, 30, and 90 phone surveys will be blinded to patients' group assignment. Staff nurses will not be blinded as to which patient the attending nurse is caring for. The PIs will not be blinded to subject treatment assignment as they will need to assure subject assignment is preformed correctly. Patients will not be formally blinded to their arm assignment, though patients may not realize that alternative models of care exist on the Vascular Neurology service. Waiving consent upon admission will help maintain patients' blinding. During the first follow up phone call, as part of the consenting process, we will specify that we are comparing different nursing styles of care. The interviewer preforming follow up phone calls and collecting data from the patient electronic medical record will be blinded to study group assignment.

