7.5 Subject Population(s) for Analysis

The entire subject population who undergo treatment assignment will be studied primarily via intention to treat analysis comparing data from follow up phone calls between groups. An as-treated analysis will also be performed.

Analysis will be performed on some pre-defined subgroups where we may expect to see effect modification: major stroke vs. minor strokes (NIHSS \leq 5), multiple medications vs. few medications, patients who were admitted following a recurrent stroke vs. a new stroke, and hemorrhagic stroke vs. ischemic stroke subtypes.

8 Safety and Adverse Events

This protocol is extremely low risk as it assigns patients to already existent forms of inpatient care. This study does not include any experimental treatment. Given there is no proposed intervention or proposed management beyond two existing forms of standard clinical care, the routine collection of adverse events is not relevant, as those will be part of routine care. However, there may be a difference between the two arms in terms of specific events of interest. These specific events of interest include falls, aspiration pneumonia, and subsequent (post-discharge) major cardiovascular and cerebrovascular events (MACCE) including stroke (ischemic, hemorrhagic, or unknown), myocardial infarction, and death of any cause. Transfers to a higher level of care (e.g. to the Neuro ICU or medical ICU from the floor) that occur as part of routine care will also be considered events of interest. We will also report any unanticipated events.

All of the aforementioned events of particular interest will be assessed while the subject is in the hospital in keeping with standard clinical care. During follow up phone calls, the interviewee will ask patients and/or their family members specifically about the occurrence of MACCEs including and death of any cause.

The safety of each mode of nursing care while the subject is in-house will be tracked using the quality control processes that are already in place as part of standard inpatient care.

9 Study Administration, Data Handling and Record Keeping

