The data that is collected will have a unique code assigned by the investigator when it is acquired to code each subject at the time of data harvesting to ensure duplicate data is not collected and PHI is protected. This unique case number will not be possible to link to any other information pertaining to each subject. By doing this, the patients' privacy will be protected. Patients' names and medical record numbers will be coded and kept separately from the database in a password protected file. The PI will ensure that data is coded correctly so that PHI is protected.

All data will be maintained on a password protected computerized database on a computer that will have a protected login. No data in the database will contain PHI as each subject will have been assigned a unique code at the time of data acquisition. The coded identifiers list will be stored in a password protected file separate from the main database in a computer that requires a unique university ID to access.

Only the PIs and the clinical research team will have access to the database. Only the PIs will have access to the coded identifier list so as to minimize the risk of a confidentiality breach. Confidentiality of the data will be ensured for as long as it is kept.

9.3 *Records Retention*

Any patient data will be held only until data analysis is complete. Once data is no longer needed for research, it will be electronically destroyed in a way that leaves no trace. Both the coded-identifiers list as well as the data set will be destroyed.

10 Study Monitoring, Auditing, and Inspecting

10.1 *Study Monitoring Plan*

Results of follow up phone calls will be discussed with the PIs on a weekly basis. The PI will review all data that is collected via REDCap. Data will be collected over the course of 6 months, cleaned for a month and analyzed for another month. The Investigator will also ensure that the monitor or other compliance or quality assurance reviewer is given access to all the above noted study-related documents and has adequate space to conduct the monitoring visit.

10.2 *Auditing and Inspecting*

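### Section 6.5 lets unblinded PIs discontinue patients for not adhering to an intervention only one arm receives, and nothing says those patients are still called or analysed

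*Combined protocol and SAP*

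**What the plan says.** Section 6.5 (Subject Withdrawal): "Patients may also be discontinued from the study at the discretion of the PIs for lack of adherence to intervention or study procedures". The same paragraph adds difficulty obtaining follow-up, unexpected events, violation of the study plan, safety and administrative reasons. It sets no criteria and no timing. It requires a record of whether each patient completes the study, but not of the reason.

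On who decides, and what they can see:
- 5.3: "The PIs will not be blinded to subject treatment assignment as they will need to assure subject assignment is preformed correctly".
- 10.1: "Results of follow up phone calls will be discussed with the PIs on a weekly basis". The PI also reviews all data entered in REDCap.
- 9.2: "Only the PIs will have access to the coded identifier list".

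On who has something to adhere to:
- 3.1.2 (Study Intervention Phase): "Patients assigned to routine care will not interact with the attending nurse".
- 5.1: the attending nurse logs tasks and time for each of her patients, so low exposure is visible in her arm.

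On follow-up and analysis:
- 7.5: "The entire subject population who undergo treatment assignment will be studied primarily via intention to treat analysis", using data from the follow-up calls. An as-treated analysis is also planned.
- 6.5.1: among patients who stop early, continued calls are promised only for those who leave against medical advice. Data are expunged when the patient asks to be removed.
- 6.6: there are no early termination visits or calls.

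**The concern.** The wording concerns discontinuation from the study, not from the attending nurse's care. A patient who engages little with the nurse can therefore lose the follow-up calls as well as the intervention. Routine-care patients have no added intervention, so they can hardly be discontinued on this ground.

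The primary outcomes are stroke knowledge (SPER) and self-reported medication adherence (MMAS-4). Patients who do not engage with an education intervention could plausibly score low on both. If they drop out of one arm only, that arm looks better with no true effect. The t-test and chi-square test in 7.4 are unadjusted and no missing-data method is given, so nothing in the analysis would correct this. The deciders know the arm and, from day 7 onward, can know the patient's answers.

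**Working it through.** **Step 1. What the sections allow, by timing of removal.**

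| Removal decided | Information available | Data that can be lost |
|---|---|---|
| Before the day-7 call | Arm and the nurse's exposure log; no call results | Days 7, 30 and 90 |
| After the day-7 call | Arm, exposure and day-7 scores | Calls still to come (days 30 and 90); day-7 data already held |

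The second row follows because 6.5.1 deletes data only at the patient's request and 7.5 covers everyone assigned. Removal that depends on a patient's own results therefore cannot touch day 7, one of the two primary time points in 7.1. Removal based on exposure can.

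**Step 2. Inputs for an illustration.** From 7.3: 65% control adherence, a 15-point improvement sought (read as absolute), 186 per arm. The sidedness of alpha is not stated; two-sided 5% is used here. The plan's sample size does not reproduce: 65% versus 80%, two-sided 5%, 80% power gives 138 per arm, and 186 gives about 90% power. That is a separate matter. Here 186 serves only as the planned arm size. Two inputs are assumptions with no source in the documents: the share removed (5% or 10%) and the adherence *a* of those removed.

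**Step 3. Apparent adherence with no true effect.** Let k be the number removed from the attending-nurse arm:

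p₁ = (186 × 0.65 − k·a) / (186 − k), with 186 × 0.65 = 120.9.

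- 10% removed (k = 18.6), a = 0.65: (120.9 − 12.09)/167.4 = 65.0%, bias 0.
- 10% removed, a = 0.40: (120.9 − 7.44)/167.4 = 67.8%, bias +2.8 points.
- 10% removed, a = 0: 120.9/167.4 = 72.2%, bias +7.2 points.

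**Step 4. Rejection rate.** SE = √[p₁(1−p₁)/(186−k) + 0.65 × 0.35/186], and the rejection rate is about Φ(−1.96 + bias/SE) + Φ(−1.96 − bias/SE). For 10% removed at a = 0.40: SE = √(0.001305 + 0.001223) = 0.0503, bias/SE = 0.55, rate = Φ(−1.41) + Φ(−2.51) = 8.5%.

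| Removed | a | Apparent rate | Bias (points) | Type I error |
|---|---|---|---|---|
| 5% | 65% | 65.0% | 0 | 5.0% |
| 5% | 40% | 66.3% | +1.3 | 5.8% |
| 5% | 30% | 66.8% | +1.8 | 6.6% |
| 5% | 0% | 68.4% | +3.4 | 11% |
| 10% | 65% | 65.0% | 0 | 5.0% |
| 10% | 40% | 67.8% | +2.8 | 8.5% |
| 10% | 30% | 68.9% | +3.9 | 12% |
| 10% | 0% | 72.2% | +7.2 | 31% |

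The figures apply to any time point at which the removed patients' data are missing. If they are kept and followed, this source of bias is zero.

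**The case against.** A reader might infer that 6.5 flatly contradicts 7.5, so that intention to treat is already broken. The text does not go that far. Section 6.5 never says that discontinued patients leave the analysis set, and 7.5 covers all who are assigned. What is at risk is the data from calls not yet made, and the documents do not say whether those calls stop.

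A reader might also see a contradiction with 5.5: "Incomplete response at 7 days will not preclude a phone call directed to patients at 30 and 90 days". This is a tension only. One incomplete call is not persistent failure to reach a patient, and the ground of difficulty obtaining follow-up applies to both arms. So do study procedures and violation of the study plan. The one-arm argument rests on adherence to the intervention alone.

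On frequency, 1.2.1 reports that no patient refused the attending nurse in 3–4 months of use, and the nurse comes to the inpatient. Removal of 5–10% may therefore never happen. Direction is also open: she visits on weekdays only (5.2), so low exposure could reflect a short or weekend stay, not a less adherent patient. Reading the top row of 31% as an expected error rate would be wrong, because it needs about 19 removals with every removed patient non-adherent.

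All of this stands and limits the claim. It does not close the gap. Leaving against medical advice is the only early stop for which continued calls are promised, and experience of refusals in routine use does not bound a discretionary rule without criteria.

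**Conclusion.** The concern holds as a permitted risk. Unblinded PIs may end a patient's participation on a ground that in practice bears on one arm, and no section protects that patient's later calls or place in the analysis. Exposure-based removal before day 7 could affect all time points; removal after sight of results could affect only days 30 and 90. Under the assumptions shown, the effect on MMAS-4 adherence runs from none, through +2.8 points with 8.5% type I error, to an extreme of +7.2 points with 31%, just under half of the 15 points sought. The documents fix neither the share removed nor the adherence of those removed, so no single figure can be called expected. SPER would be exposed in the same way, but no size is offered for it here.

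**What to change.** In 6.5, delete lack of adherence to the intervention as a ground for discontinuation from the study. Leave the safety and administrative grounds in place. Then add:

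1. Low exposure, or any discontinuation by a PI, does not end the day 7, 30 and 90 calls unless consent is withdrawn. It does not remove the patient, or data already collected, from the assigned arm in the 7.5 intention-to-treat set.
2. The reason for each discontinuation is recorded and reported by arm.
3. Low exposure is used only in the as-treated analysis already planned.
4. Discontinuation decisions are made without sight of that patient's outcome scores. Reducing the weekly discussion to completion counts would not achieve this alone, because 10.1 has the PI review all REDCap data.

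The cost is protocol wording and a reason field on the form; no extra patients or calls beyond those planned are needed. The downside is that poorly exposed patients stay in the comparison, so the estimated effect may be slightly smaller. It would then be the intention-to-treat effect that 7.5 sets out to estimate.

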6.5.1 Data Collection and Follow-up for Withdrawn Patients

If patients decide to stop participating in inpatient care when recommended by the treating team, documentation for patient decisions against medical advice (AMA), this will be documented in keeping with standard practice. Follow up phone calls will still be sought on patients who leave AMA. Patients who are lost to follow up or decline to participate in follow up phone calls and do not consent to data abstraction from the inpatient record will not have any further data collected.

Patients who request to be removed from the study will have all available data expunged.

6.6 Early Termination Visits

We will not perform early termination visits or early phone calls.

7 Statistical Plan

7.1 Primary Endpoint

The primary endpoint for this study will be a comparison of the mean scores on the SPER and the rate of adherence on the MMAS-4 (score < 2) and the SPER between groups at 7 and again at 90 days.

Scores on the MMAS-4 and SPER will be calculated per protocol. On the MMAS-4, affirmative answers will receive a point and negative answers will be assigned zero. The total score will be the sum of the answer to all four questions. The SPER, question 1 and 2 are scored as follows: 0 = no correct content in response to the question, 1 = the patient provided some but not all of the correct content in response to the question, and 2 = patient provided all key content in response to the question. Question 3-5 were scored as follows as 0 = no correct content in response to the question and 2 = the patient provided the correct response to the questions. A score of 10 indicates all correct responses to the key content.

The SIS is a patient-based, self-report scale in which each item is rated in a 5- point Likert scale in terms of the difficulty the patient has experienced in completing each item. A score of 1 = an inability to complete the item and a score of 5 = no difficulty experienced at all. Using an algorithm, summative scores are generated for each domain.

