1.1 Background and Relevant Literature

Every year, approximately 610,000 people experience a first stroke and another 185,000 have a recurrent stroke in the United States.² Further, among 307,887 ischemic stroke patients in a Medicare database, 14% were readmitted to hospitals within 30 days of discharge.³ Stroke patients are thus a high risk population worthy of increased treatment interventions to prevent early complications. Patients with recurrent stroke have poorer outcomes and higher healthcare costs than those with first stroke.⁴ Despite the substantial burden of recurrent stroke, many patients with prior strokes are ill informed about stroke risk factors and have suboptimal personal health behaviors.^{5,6} Existing care delivery models thus may not optimally aligned with stroke patients' needs and goals.

Poor adherence to prescribed medications following hospital discharge likely plays an important role in stroke recurrence, disability, other complications, and death.⁷ In the largest observational study of medication compliance following stroke, the Adherence eValuation After Ischemic stroke–Longitudinal (AVAIL) registry, independent predictors of 1-year medication persistence included fewer medications prescribed at discharge, having an adequate income, having an appointment with a provider, and a greater understanding of why medications were prescribed and possible side effects.⁸ Earlier studies have also noted that inadequate care transitions and poor patient–provider communications contribute to medication non-adherence.⁹ Unfortunately, no educational or organizational interventions have clearly been shown to effectively improve adherence to secondary stroke prevention strategies.¹⁰

Attending Nurse

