2.1 Primary Objective

- To determine whether patients report better understanding of stroke facts and medication adherence when cared for by an attending nurse compared to routine nursing care.

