To compare the two models of nursing care, we will survey all patients directly about the care they receive in the hospital once they are discharged. Surveys tools designed to ascertain medication adherence, disease specific knowledge, as well as satisfaction with care and hospital readmissions will be assessed at 7, 30, and 90 days via follow-up structured telephone interviews. We will consider the 7 day follow-up phone call the baseline assessment. The Morisky scale (MMAS-4),¹⁵ a well validated tool that has been studied in stroke victims,¹⁶ will be used to determine medication adherence. The Stroke Patient Education Retention (SPER)¹⁷ tool will be used to assess patient knowledge. The Stroke Impact Scale (SIS)¹⁸ will be used to evaluate self-perception of stroke deficits by patients. Thirteen other survey questions designed specifically for this study will also be posed to patients at 7, 30 and 90 days from follow up along with two overall quality of life questions at 7 and 90 days. As a secondary outcome, we will calculate and then use a global statistic as a general marker for success to compare the effectiveness of each nursing care model in improving patients' overall outcomes.¹⁹ All interviews will be performed by a trained research assistant who will not be involved in the inpatient care of patients and will be blinded to study allocation. Subject participation will conclude after 90 days.

We will request a waiver of consent for initial enrollment in this study. Follow-up calls to patients will explicitly state according to an IRB-approved script that the questions are part of a research study. Patients will also be asked if they consent to collection of data from their medical record as part of the study. Patients will have the option to participate or decline. If they choose to participate in the interview survey and allow collection of data from their recent hospitalization, then the study will proceed with their verbal consent.

If they decline to participate in the interview survey, then no further study specific tools will be used, but they will be asked if they consent to chart abstraction. However, patients cannot participate in interviews without agreeing to data collection. Patients can decline to participate in both the interviews and allow for data collection. If they fully decline to participate in the study, their data will be expunged and no further data collected.

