3.2 Study Endpoints

3.2.1 Primary Study Endpoints

- Primary endpoints will be stroke education retention as measured by the SPER and medication adherence as measured by MMAS-4 as these are the areas where we anticipate the largest potential effect of the nurse attending. The mean scores on these two tests will be compared between groups at each time interval that they are administered.

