7.3 Sample Size and Power Determination

For this pilot project, we anticipate that 65% of patients in the control arm will be adherent to medications (MMAS-4 < 2) based on literature reporting 60%¹⁶ adherence as evaluated using these scales in stroke patients and 70%²¹ adherence in patients with hypertension. To achieve success on the primary endpoint, we estimate that patients must improve to by 15% in order to make this intervention worthy of future investigation in a larger study. Assuming an alpha of 0.05 and a power of 80%, with a 1:1 assignment to each arm, we will require 186 patients in each arm for a total of 372 patients. With that number of patients

we will be able to powered to detect a very small difference of 0.3 (delta = .15 (SD=2)) in the mean scores of the SPER based on the published data.¹⁷ Each outcome will be evaluated independently so that we will not need to make any power readjustments. Readmission rates at 30 days are typically low⁴ and likely lower at our institution based on prior data so we will be underpowered for this outcome. Clinically differences on the SIS will depend on the initial stroke severity of patients within each group and therefore the study cannot be powered for this secondary endpoint.

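### MMAS-4 adherence is an unranked primary comparison at day 7 and day 90, although day 7 is a weak measure of adherence after discharge and the 65% planning rate is tied to neither time

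*Combined protocol and SAP*

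**What the plan says.** Section 7.1 compares "the rate of adherence on the MMAS-4 (score < 2) and the SPER between groups at 7 and again at 90 days". It neither ranks the two times nor says whether success is needed at one or both. Section 3.2.1 differs: "The mean scores on these two tests will be compared between groups at each time interval that they are administered". For the MMAS-4 that adds day 30, since section 6.3.2 states: "At 30 days following hospital discharge, the SIS and the MMAS-4 will be administered". It also makes the quantity a mean score, whereas 7.1 and 7.4 use a proportion.

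Table 1 (Schedule of Study Procedures) sets the first call at "7 from discharge (+/- 3 days", that is, days 4 to 10. Section 3.1 says of this call: "We will consider the 7 day follow-up phone call the baseline assessment".

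In 7.3, "we anticipate that 65% of patients in the control arm will be adherent to medications", a figure set between 60% reported in stroke patients and 70% in hypertension patients. Neither that rate nor the 186 per arm is attached to a call. The same section evaluates each outcome on its own and makes no adjustment.

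The objective in 2.1 is whether "patients report better understanding of stroke facts and medication adherence" under the attending nurse, with no time stated. The rationale in 1.1 is: "Poor adherence to prescribed medications following hospital discharge likely plays an important role in stroke recurrence, disability, other complications, and death".

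**The concern.** The rationale concerns medication-taking once patients are home, and 1.1 supports it with a registry of one-year persistence. At the first call a patient has at most 4 to 10 days of such behaviour to report. The plan gives no reference period for the four yes/no items and no reason for choosing day 7 for adherence. One section treats the call as baseline and another as a primary outcome, and a measurement taken after the intervention has ended cannot sensibly be both.

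With no ranking, adherence has two chances of success. A difference seen only in the first days at home could be reported as a positive primary result even if day 90 disagrees, and an early null could be read as failure. The power statement does not say which of the two comparisons it describes.

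**Working it through.** **Inputs.** Control 65%, gain 15% (read as percentage points, so 80%), alpha 0.05 (two-sided assumed), 80% power, 1:1 allocation, 186 per arm (all 7.3); Pearson chi-square (7.4); times from 7.1 and Table 1. The documents give no day-7 adherence rate and no correlation between calls, so both are varied as assumptions.

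**1. The plan's own figure.** n per arm = [1.960·√(2p̄(1−p̄)) + 0.842·√(p₁(1−p₁)+p₂(1−p₂))]² / (p₂−p₁)². With p₁ = 0.65, p₂ = 0.80 and p̄ = 0.725, this gives 138 (151 with continuity correction). The stated 186 does not reproduce from its stated inputs, which is a separate matter. Taking 186 as given:

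- SE under the null = √(2 × 0.725 × 0.275 / 186) = 0.0463
- SE under the alternative = √((0.65 × 0.35 + 0.80 × 0.20) / 186) = 0.0456
- Power = Φ[(0.15 − 1.960 × 0.0463) / 0.0456] = Φ(1.30) = 90%

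This is the benchmark. It applies to whichever call has 65% control adherence.

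**2. Power if day-7 control adherence is higher (assumption).** The planned odds ratio is (0.80/0.20) / (0.65/0.35) = 2.15. At 75% control, for example, the odds are 3 × 2.15 = 6.46, so the intervention rate is 86.6%. Two other ways of carrying the effect over are shown: the planned relative cut in non-adherence (35% to 20%, ratio 20/35) and a fixed 15-point gain.

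| Control rate | Intervention rate at OR 2.15 | Power, OR 2.15 | Power, relative cut | Power, +15 points |
|---|---|---|---|---|
| 65% | 80.0% | 90% | 90% | 90% |
| 70% | 83.4% | 86.7% | 83.5% | 93.7% |
| 75% | 86.6% | 81.3% | 74.1% | 97.0% |
| 80% | 89.6% | 73.4% | 62.3% | 99.3% |
| 85% | 92.4% | 62.0% | 48.5% | would need 100% |
| 90% | 95.1% | 46.4% | 33.5% | impossible |

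**3. Two unranked tests.** If there is no effect at either time and each test is at 0.05:

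- Independent results: 1 − 0.95² = 9.75%.
- Correlation 0.7 between the two test statistics (bivariate normal): 8.3%.

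The range is therefore about 8-10%. It counts a false difference in either direction; under independence the part favouring the attending nurse is 1 − 0.975² = 4.9%. If 3.2.1 governs and day 30 is added, the independent figure is 1 − 0.95³ = 14.3%.

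**4. Sections side by side.** For the MMAS-4, 3.1 makes the day-7 call baseline; 3.2.1 makes the mean score primary at days 7, 30 and 90; 7.1 makes the proportion below 2 primary at days 7 and 90; 7.3 plans for a proportion at no stated time. These cannot all be followed.

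**The case against.** The best defence is that day 7 belongs to the question. Section 2.1 names no time, the Study Summary lists 7, 30 and 90 days, and the intervention is aimed at the transition home, so early adherence is a legitimate thing to compare. Day 90 is already primary in the same sentence and would be reported beside it. All of this stands. A reader might infer that the day-7 comparison cannot answer the trial's question; the documents do not support that. A wrong control rate alters power, not validity.

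A reader might also infer that a null at day 7 is built in, through a ceiling or because patients answer from habits before admission. The documents give neither a recall period nor an early adherence rate, so both mechanisms are assumptions. At the planned odds ratio power stays above 80% up to 75% control adherence, and a fixed 15-point gain becomes easier to detect up to 80%.

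Nor do the documents show that the 65% comes from patients with long-established disease. The 60% is described as from stroke patients, with no time since the event, and the trial itself admits recurrent strokes. Only the 70% is plainly from a non-stroke group.

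Finally, the missing reference period affects day 90 too, so changing the time point does not cure it. That is correct, but by then far more post-discharge medication-taking is available to report. The defence does not answer the missing ranking, the baseline label or the untied planning rate.

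**Conclusion.** The concern holds in a limited form. Day 7 is a valid comparison of early self-reported adherence but a weak and unjustified primary measure of adherence after discharge. It shares primary status with day 90 without ranking, at a call that the protocol elsewhere calls baseline, and with no power statement tied to it.

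The false-positive chance for adherence is about 8-10% rather than 5%, for an assumed correlation of 0.7 to 0. The loss of power at day 7 is conditional: none if control adherence is 65%, and a fall from 90% to between 81% and 46% if it is 75% to 90% and the planned odds ratio applies. These power figures also assume that all 186 per arm are analysed. The point is of moderate weight: it should be settled before outcome data are analysed, but it does not undermine the trial.

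**What to change.** - In 3.2.1 and 7.1, name the day-90 proportion with MMAS-4 below 2 as the single primary adherence endpoint, and report the day-7 and day-30 MMAS-4 as supportive.
- In 7.3, state that the 65% applies to day 90 and add a sensitivity range around it.
- Reconcile 3.1 (baseline label), 3.2.1 (mean scores at every administration) and 7.1 (proportion at days 7 and 90).
- State the period that the MMAS-4 answers are taken to cover at each call.
- SPER may stay at day 7, because knowledge can be measured then.

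The cost is wording only, since every measurement is already scheduled. The planning calculation is unchanged if 65% holds at day 90. The downside is that the primary adherence result then rests on the last call, where somewhat more responses are likely to be missing.
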